### **3.5 Risks and benefits**

The risk to subjects in this trial will be minimized by compliance with the inclusion/exclusion criteria, close clinical, laboratory and radiological monitoring, and application of good clinical practice principles.

## 4 Population

**Key inclusion criteria :** Biologic-naïve patients aged 18-60 years with BD fulfilling the ISG criteria, who have a recent exacerbation of large-vessel vascular disease and/or parenchymal neurologic disease.

### 4.1 Inclusion criteria

**Key inclusion criteria :** Biologic-naïve patients with BD fulfilling the ISG criteria, who have a recent exacerbation of large-vessel vascular disease and/or parenchymal neurologic disease within the last month.

**For NBS :1)** Patients experiencing an acute exacerbation of parenchymal neurologic disease involving brainstem and/or diencephalic region with in last month.

Exacerbation is defined based on the presence of both of the following:

- a. An acute/subacute neurological syndrome including any of hemiparesis, ataxia, dysarthria within the first month of onset of neurologic manifestations (without any prior high dose steroid treatment)
- b. Compatible cranial MRI lesion involving brainstem and/or diencephalic region

**2)** Patients aged over 18-60 BD fulfilling the International Study Group (ISG) criteria, who have exacerbation of large-vessel vascular disease and/or parenchymal neurologic disease *with in last month*.

#### **For Vascular Disease :**

1)Patients experiencing an acute exacerbation of vascular disease within the last month, involving

- d. Large arteries (abdominal aorta, pulmonary arteries, extremity arteries)
- e. Large veins (deep vein thrombosis of extremities, caval vein thrombosis, dural sinus thrombosis)
- f. Compatible radiological findings (spiral CT, MR, or Doppler ultrasonography)

**2)** Patients aged over 18-60 BD fulfilling the International Study Group (ISG) criteria, who have exacerbation of large-vessel vascular disease and/or parenchymal neurologic disease *with in last month*.

### 4.2 Exclusion criteria

Patients fulfilling **any** of the following criteria are not eligible for inclusion in this study. No additional exclusions may be applied by the investigator, in order to ensure that the study population will be representative of all eligible patients.

#### **Key exclusion criteria**

##### **For NBS:**

1-Presence of severe neurological sequelae from any previous attacks rendering the patient dependent on others physically or mentally

2-Any other neurological cause underlying the picture including ischemic CNS lesion on MRI

3-Any previous treatment with biological agents other than interferon-alpha or any previous treatment with cyclophosphamide

#### **For Vascular disease**

4-Presence of severe vascular sequelae from any previous attacks rendering the patient dependent on others

5-Any other vascular disease complication the evaluation of exacerbation

6-Any previous treatment with biological agents other than interferon-alpha, or any previous treatment with cyclophosphamide

#### ***General***

7- Presence or history of any other inflammatory rheumatic disease

8- Use of the listed treatment

- c. interferon-alpha in the last 6 months,
- d. IVMP in the past month

9- Positive PPD test (according to local guidance) where an active TB infection cannot be excluded via Quantiferon (T-Spot or radiographic imaging if needed) If PPD test or Quantiferon-Gold assay result shows latent TB infection without signs of active tuberculosis disease, patient will be allowed to enter in the study, when the patient agrees to start taking isoniazid prophylaxis along with the study drug for 9 months.

10- Pregnancy or lactation

11-Presence of any active or chronic infection or any major episode of infection requiring hospitalization or treatment with i.v. antibiotics within 30 days or oral antibiotics within 14 days prior to screening

12-History of a malignancy within the last 5 years, except for successfully excised squamous or basal cell carcinoma of the skin

13-Women of childbearing potential not using the contraception method(s) specified in this study, as well as women who are breastfeeding

14-With known sensitivity to canakinumab

15- Use of any other investigational agent in the last 30 days

## 5 Treatment

Treatment Arm	# of Patients Entered Treatment	Type of Study Drug	Compound	Min Dose	Max Dose	Frequency	Admin. Route	Generic Acceptable?
Canakinumab	10	Investigational	ACZ	150 mg	300 mg	Monthly	IV (SC after month 6)	-

### 5.1 Protocol requested treatment

#### 5.1.1 Investigational treatment

**Canakinumab 150 mg powder for solution for infusion/injection** contains nominally 150 mg canakinumab. The vials contain an overfill of 20% i.e. resulting in a total amount of 180 mg canakinumab per vial. The overfill will allow for complete withdrawal of the labeled amount of canakinumab.

Canakinumab will be used as 300 mg IV infusions for subjects over 18 years and diagnosed as Behcet disease. The dose will be down-titrated to 150 mg IV after first dose. And there will be a switch to 150 mg SC injections after 6 months (if investigators confirm)

#### 5.1.2 Additional study treatment

No additional treatment beyond investigational treatment is requested for this trial.

### 5.2 Treatment arms

This is a open-label, single-arm active treatment study design.

### 5.3 Treatment assignment, randomization

At Screening (Day -7 to -0) an eligible patient will be given the lowest available number. The investigator will enter the patient number on the CRF.

### 5.4 Treatment blinding

This will be an open-label, single arm study.

## **5.5 Treating the patient**

### **5.5.1 Patient numbering**

Each patient is uniquely identified by a Subject Number which is composed by the site number assigned by Novartis and a sequential number assigned by the investigator. Once assigned to a patient, the Subject Number will not be reused.

If an enrolled patient fails to be treated for any reason, the reason will be entered on the Screening Study Disposition CRF.

### **5.5.2 Dispensing the investigational treatment**

Each study site will be supplied by Novartis with investigational treatment in packaging of identical appearance.

### **5.5.3 Handling of study treatment**

#### **5.5.3.1 Handling of investigational treatment**

Study drug will be supplied to the study site by Novartis as open labelled bulk medication.

Study drugs must be received by a designated person at the study site, handled and stored safely and properly, and kept in a secured location to which only the designated study person has access. Upon receipt, all study drugs should be stored according to the instructions specified on the drug labels. Clinical supplies are to be dispensed only in accordance with the protocol.

Medication labels will be in the local language and comply with the legal requirements of country. They will include storage conditions for the drug, but no information about the patient except for the patient number.

The investigator or authorized site staff must maintain an accurate record of the shipment and dispensing of study drug in a drug accountability log. Monitoring of drug accountability will be performed by the field monitor during site visits and at the completion of the trial.

At the conclusion of the study, and as appropriate during the course of the study, the investigator will return all used and unused study drug, packaging, drug labels, and a copy of the completed drug accountability log to the monitor or to the Novartis address provided in the investigator folder at each site.

#### **5.5.3.2 Handling of other study treatment**

Not applicable.

### **5.5.4 Instructions for prescribing and taking study treatment**

All patients will receive study medication every four weeks. Patients will receive IV infusions of canakinumab in open label study treatment period. Please refer to for study schema description.

All study treatments assigned to the patient during the study will be recorded.

Each reconstituted vial provides 150 mg of canakinumab per 1 mL.

From a microbiological point of view, once the canakinumab solution for infusion has been compounded in the infusion bag or the solution for injection has been prepared, it should be used immediately. If not used immediately, it should be administered within 24 hours (end of infusion included). If the infusion solution/solution for injection is not used within 60 minutes of preparation, it should be kept at 2-8 °C. The bags and the solution for injection should be allowed to come to room temperature for 5-10 minutes but not more than 15 minutes before administration.

Detailed instructions on the preparation and administration of the study drug will be described in the Pharmacist Manual and provided to the site.

Patients should remain at the study site for observation for 1 hour following study drug administration.

### **5.5.5 Permitted dose adjustments and interruptions of study treatment**

The first dose will be started as 300 mg IV.. At the end of the first month, an analysis will be conducted to assess the complete, partial, and non-responders to canakinumab treatment by physician.

Partial responders will be able take the 2nd canakinumab dose as 300 mg IV infusion at the first month then will continue the canakinumab treatment with 150 mg IV infusions at monthly intervals for 4 times. The complete responders will continue the canakinumab treatment with 150 mg IV infusions at monthly intervals for 5 times. Non-responder or deteriorating patients will be dropped from the study at the first month evaluations.

At the end of the 6th month the administration route can be switched to subcutaneous injection.

### **5.5.6 Rescue medication**

A rescue treatment with increased doses of prednisolone or intravenous methyl prednisolone pulses could be used depending on worsening of BD manifestations at the discretion of the investigator.

If no response or worsening of neurologic/vascular manifestations were observed in the first week, rescue treatment decision should be given with the repeated CSF and MRI (neurologic) or CT/Doppler (vascular) analyses.

Following protocol will be used as rescue treatment in patients with worsening symptoms:

For patients with neurologic involvement: 5-10 days of 1000 mg intravenous methyl prednisolone, followed by 1 mg/kg/day prednisolone, if still an insufficient response is observed, 1000 mg intravenous cyclophosphamide

For patients with vascular involvement: 3 days of 1000 mg intravenous methyl prednisolone, followed by 1 mg/kg/day prednisolone, if still an insufficient response is observed, 1000 mg iv cyclophosphamide.

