## 2.1 Primary objective(s)

**Primary endpoint:** Resolution of acute exacerbation findings related to BD based on achievements in any of the following items without deterioration on day 30:

**For patients with parenchymal neurologic disease:** Resolution of acute exacerbation of parenchymal neurologic findings based on improvements in any of the following items without deterioration on Day 30:

- a. Improvement of muscle strength, ataxia, or other relevant neurologic findings depending on the involved region on neurological examination (by NBDS, Modified EDSS, and modified Rankin scores)
- b. Improvement in systemic inflammatory findings (CRP, ESR, SAA)
- c. Any decrease in the size of the MRI lesion, or disappearance of contrast enhancement
- d. Improvement in patients' and physicians global assessment using a 10-cm visual analogue scale (VAS)

**Complete response** will be defined as full clinical recovery to the pre-attack state, disappearance of MRI lesion(s), and normalisation of CSF findings.

**Partial response** will be defined as partial improvement in clinical findings, but with findings still worse than the pre-attack state, and MRI lesions, which become smaller with no or less enhancement, and a decrease in CSF cell count.

**Non-response** will be defined as no improvement in clinical findings, no change on MRI, no change in CSF parameters, or worsening in those findings.

**For patients with large vessel vascular disease:** Resolution of acute vascular exacerbation findings related to BD based on achievements in any of the following items without deterioration at 1 month:

- a. Improvement in relevant symptoms (localised pain, abdominal pain, calf thickness, haemoptysis) by using physician and patient's global assessment with VAS
- b. Improvement in systemic inflammatory findings (CRP, ESR, SAA)
- c. Any improvement in radiological findings depending on the involved vessels (MR, CT or Doppler findings)
- d. Improvement in patients' and physicians global assessment using a 10-cm visual analogue scale (VAS)

**Complete response** will be defined as clinical and laboratory improvement based on  $\geq 50\%$  improvements in patient's and physician's global assessments by using VAS, and  $\geq 50\%$  reduction in CRP values; along with stable or  $\geq 20\%$  reduced aneurym size in patients with arterial involvement, and stable or  $\geq 20\%$  reduced calf swelling in patients with lower extremity venous thrombosis.

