### **5.5.8 Prohibited Treatment**

The following treatments are NOT allowed prior to baseline (time intervals prior to baseline are detailed below) AND during the entire study:

- Etanercept in the 4 weeks prior to the baseline visit (Day 0) and thereafter
- Riloncept in the 3 weeks prior to the baseline visit (Day 0) and thereafter
- Adalimumab in the 8 weeks prior to the baseline visit (Day 0) and thereafter
- Infliximab in the 12 weeks prior to the baseline visit (Day 0) and thereafter
- Rituximab in the 26 weeks prior to the baseline visit (Day 0) and thereafter
- Any other investigational biologics in the 8 weeks prior to the baseline visit (Day 0) and thereafter (with the exception of anakinra therapy –see below)
- Kineret (anakinra therapy) 3 days prior to the baseline visit (Day 0) and thereafter
- Leflunomide in the 4 weeks prior to the baseline visit (Day 0) and thereafter. After the completion of leflunomide treatment a cholestiramine in dose 8 g 3 times per day for 14 days is recommended.
- Thalidomide in the 2 weeks prior to the baseline visit (Day 0) and thereafter
- Cyclosporine in the 2 weeks prior to the baseline visit (Day 0) and thereafter
- i.v. immunoglobulin (i.v. Ig) in the 8 weeks prior to the baseline visit (Day 0) and thereafter
- 6-Mercaptopurine, cyclophosphamide, or chlorambucil in the 12 weeks prior to the baseline visit (Day 0) and thereafter
- Dapsone, in the 3 weeks prior to the baseline visit (Day 0) and thereafter
- Corticosteroids  $\geq 20\text{mg/day}$  or  $>0.4 \text{ mg/kg}$ , whichever applies, in the 1 week prior to the baseline visit (Day 0) and thereafter
- Live vaccinations within 3 months prior to the start of the trial, during the trial, and up to 3 months following the last dose.
- Use of other investigational non-biological drugs at the time of enrollment, within 30 days or 5 half-lives of enrolment, whichever is longer.
  - Intravenous methyl prednisolone pulse treatment within the last month

The investigator should instruct the patient to notify the study site about any new medications he/she takes after the start of the study drug. All medications and significant non-drug therapies (including physical therapy and blood transfusions) administered after the patient starts treatment with study drug must be listed on the Concomitant medications/Significant non-drug therapies after start of study drug.

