### **5.5.9 Discontinuation of study treatment**

Study drug must be discontinued for a given patient if the investigator determines that continuing it would result in a significant safety risk for that patient. The following circumstances require study drug discontinuation:

- Emergence of the following adverse events:
  - in the case of any severe or serious adverse event that is not compatible with administration of study medication, including adverse events that require treatment with an unacceptable co-medication,
  - in the case of onset of malignancy,
  - in the case of an uncontrolled life-threatening infection.
- Pregnancy
- Use of the prohibited concomitant medications
- Withdrawal of informed consent

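### High-dose steroid rescue is allowed from week 1, but nothing visible says how a patient rescued before Day 30 is classified, and the rescue section conflicts with the prohibited-medication rules

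*Combined protocol and SAP*

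**What the plan says.** **Rescue.** Section 5.5.6 says that "increased doses of prednisolone or intravenous methyl prednisolone pulses could be used depending on worsening of BD manifestations", at the investigator's discretion. It also sets an early trigger: "If no response or worsening of neurologic/vascular manifestations were observed in the first week, rescue treatment decision should be given", supported by repeat CSF and MRI (neurologic) or CT/Doppler (vascular). The regimen is 1000 mg IV methylprednisolone daily, for 3 days in vascular and 5-10 days in neurologic patients. Prednisolone 1 mg/kg/day follows, then 1000 mg IV cyclophosphamide if the response is still insufficient.

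**Response.** Sections 2.1 and 5.9.1 define the primary endpoint by "achievements in any of the following items without deterioration on day 30", and then define complete, partial and non-response from clinical, laboratory, imaging and (neurologic) CSF findings. Section 5.5.5 has the physician "assess the complete, partial, and non-responders to canakinumab treatment by physician" at month 1, and adds: "Non-responder or deteriorating patients will be dropped from the study at the first month evaluations".

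**Analysis.** Section 8.4.1 lists the percentage of complete responders first among the primary variables. Section 8.4.2 compares every parameter with baseline and ties the efficacy claim to a response of 50% or more in half or more of the patients. Section 8.1 defines the ITT set as everyone who took a dose, and a per-protocol set of completers without major deviations.

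**Restrictions.** Section 5.5.8 bars corticosteroids at 20 mg/day or more, or above 0.4 mg/kg, "whichever applies, in the 1 week prior to the baseline visit (Day 0) and thereafter". It also bars "cyclophosphamide, or chlorambucil in the 12 weeks prior to the baseline visit (Day 0) and thereafter". Section 5.5.9 lists "Use of the prohibited concomitant medications" among the events that require canakinumab to stop. Section 5.9.4 rules out any rise in prednisolone during the trial.

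**The concern.** The study has one arm and judges each patient against baseline, so no control group can separate a steroid effect from a canakinumab effect. Eligibility already treats recent pulses as a confounder: IV methylprednisolone in the past month is an exclusion (4.2), and a neurologic attack must not have been treated with high-dose steroid beforehand (4.1). After baseline, no matching rule protects the endpoint.

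Two things are at stake. The first is the primary result: a response reached after several grams of methylprednisolone is not evidence for canakinumab, yet it could count towards the claim. The second is conduct: a site that follows 5.5.6 breaches 5.5.8 and 5.9.4 as they are worded, and the sections do not refer to one another.

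**Working it through.** The plan gives no figure to reproduce: 8.7 sets 10 patients without a calculation, and no rescue rate is stated. The check compares the sections and then counts patients.

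**1. Can rescue come before the assessment?** Yes. The decision can fall in the first week; the first scheduled efficacy assessment is Day 30 (assessment schedule). Methylprednisolone totals:
- vascular: 3 × 1000 mg = 3 g
- neurologic: 5 × 1000 mg = 5 g to 10 × 1000 mg = 10 g

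**2. Does any class depend on rescue?** No visible one does.
- *Vascular complete response* needs patient and physician VAS and CRP to improve by about half (at least 50% in 2.1, more than 50% in 5.9.1), with aneurysm size or calf swelling stable or reduced. A patient whose symptoms and CRP fall after pulses, with calf swelling no worse than baseline, satisfies this.
- *Neurologic complete response* needs full recovery, no remaining MRI lesion and normal CSF. That is hard to reach by Day 30 through rescue.
- *Partial response* in vascular disease is 20-49% improvement in 2.1 (20-50% in 5.9.1), so it essentially falls below the 50% bar in 8.4.2.

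**3. Does stopping canakinumab settle the class?** No. Doses are scheduled on Days 0 and 30, so stopping after an early rescue withholds nothing before the Day 30 assessment. Neither 5.5.9 nor 8.4 equates discontinuation with non-response. Section 5.5.10 has data up to study discontinuation analysed but assigns no class. The patient stays in the ITT set.

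**4. Effect on the 50% aim.** Let n = 10, let u be the unrescued responders, and let k be the rescued patients counted as responders. The aim needs 5 of 10. The classification rule changes the conclusion when u < 5 and u + k ≥ 5.

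| k | u for which the conclusion changes | Example |
|---|---|---|
| 1 | 4 | 4/10 becomes 5/10 |
| 2 | 3 or 4 | 3/10 becomes 5/10 |
| 3 | 2, 3 or 4 | 2/10 becomes 5/10 |

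Each patient is worth 1/10 = 10 percentage points.

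**5. Rescue against the restrictions.**

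| 5.5.6 prescribes | Other section |
|---|---|
| Prednisolone 1 mg/kg/day | 5.5.8 limit of 0.4 mg/kg; 1 / 0.4 = 2.5 times the limit |
| Methylprednisolone 1000 mg/day | 5.5.8 limit of 20 mg/day; 1000 / 20 = 50 times that figure, before any conversion between steroids |
| Cyclophosphamide 1000 mg | Prohibited by 5.5.8 |
| Higher prednisolone dose | Ruled out by 5.9.4 |
| Any of the prohibited drugs above | Canakinumab must stop under 5.5.9 |

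Sections 5.5.8 and 5.9.4 carry no rescue exception.

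**The case against.** The best defence is that the protocol already points towards non-response. The rescue regimen is meant for patients whose symptoms worsen, worsening is one of the non-response criteria, and deteriorating patients leave at month 1. The physician judges response to canakinumab specifically. Attack status, VAS, global assessments, neurological examination and imaging are scheduled on Days 7 and 14, so early worsening would be on record. All of this is true, and a careful physician may well classify a rescued patient as a non-responder. But the drop-out decision is made at the month 1 evaluation, the endpoint's no-deterioration condition is tied to Day 30, and 8.4.2 compares with baseline. No line says that rescue or week-1 worsening decides the class.

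The per-protocol set also limits the harm, since a rescued patient who must stop treatment would ordinarily not be a completer. That removes the patient from one presentation; it does not classify the patient in the ITT result. The study is also exploratory and unpowered, which lowers the stakes, although 8.4.2 still sets a condition for claiming efficacy.

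A reader might infer that a rescued patient called a Day 30 responder simply continues canakinumab under 5.5.5 and enters the steroid taper. The documents do not support that: 5.5.8 and 5.5.9 read together require canakinumab to stop. A reader might also infer that partial responses after rescue inflate the 50% claim. They essentially fall below that bar.

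**Conclusion.** The gap is real and should be closed before the Day 30 data are analysed. As written, early rescue followed by improvement can be counted as an ITT response, mainly as vascular complete response. One such patient is enough to change the conclusion if four unrescued patients respond. Separately, 5.5.6 contradicts 5.5.8 and 5.9.4, and it triggers 5.5.9 without saying so.

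This rests on 10 treated patients (3.1 says approximately 10) and on reading the 50% bar as a count of complete responders, in line with 8.4.1. It also rests on the visible text: 8.1 contains a redaction that could hold further analysis detail. The split between vascular and neurologic patients and the rescue rate are not given. A reader might infer that the gap makes a false claim likely, but the documents support only the possibility, not a probability.

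**What to change.** 1. **Classification.** Add to 5.9.1 and 8.4.2: *A patient who receives rescue under 5.5.6 for the neurologic or vascular attack before the Day 30 assessment is a non-responder in the primary ITT analysis; all treated patients are in the denominator.* Report the number rescued beside the response rate, and give the response as assessed as a sensitivity result.
2. **Consistency.** Refer to 5.5.6 in 5.5.8 and 5.9.4 so that rescue is a stated exception. Confirm in 5.5.9 that canakinumab stops after rescue, which is what the current text yields, unless the sponsor decides otherwise on safety grounds.

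**Cost.** Item 1 is amendment wording, with no added patients or visits. Steroid use is assessed at every visit, and concomitant medication is recorded with its reason (5.5.7, 5.8). The CRF is not among the documents, so check that it captures the rescue start date. The primary response rate falls by any patient who improves only after rescue. Item 2 needs a safety decision as well as wording, in a study without a data monitoring committee (7.4). If canakinumab stops, rescued patients add little to the 12-month endpoints; if the sponsor lets it continue, it is given alongside high-dose steroid and possibly cyclophosphamide.

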**Partial response** will be defined as clinical and laboratory improvement based on observations of an improvement between 20-49% according to patient's and physician's global assessments by using VAS, 20-49% reduction in CRP values; along with stable or less than 20% reduced aneurym size in patients with arterial involvement, and stable or less than 20% reduced calf swelling in patients with lower extremity thrombosis.

**Non-response** will be defined as observing no or less than 20% clinical improvement by patient's and physician's global VAS or worsening of clinical findings, no change or increase in acute phase response, increase in aneurysm size for patients with arterial involvement or progression of venous thrombosis in patients with venous involvement.

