### **3.4 Purpose and timing of interim analyses/design adaptations**

At the end of 1st month primary end point will be assessed by the physician. Complete / Partial / Non responders will be determined.

At 3rd and 6th months, there will be additional analyses to evaluate steroid tapering, prevention of disease exacerbation, and general disease activity by physician.

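### Steroid rescue is allowed from about week 1, but nothing says how it affects Day 30 response, and 5.5.6 conflicts with 5.5.8 and 5.9.4

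*Combined protocol and SAP*

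**What the plan says.** Section 5.5.6 opens by allowing more prednisolone or methylprednisolone pulses when the disease worsens, at the investigator's discretion and with no earliest day. It then says "If no response or worsening of neurologic/vascular manifestations were observed in the first week, rescue treatment decision should be given", supported by repeat CSF and MRI, or CT/Doppler. The fixed regimen is introduced with "Following protocol will be used as rescue treatment in patients with worsening symptoms". For neurologic patients it is "5-10 days of 1000 mg intravenous methyl prednisolone, followed by 1 mg/kg/day prednisolone". Vascular patients get 3 days of pulses and the same oral dose. In both groups 1000 mg cyclophosphamide follows if response is still insufficient.

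The primary endpoint in 2.1 (repeated in 5.9.1) is "Resolution of acute exacerbation findings related to BD based on achievements in any of the following items without deterioration on day 30". Neurologic non-response is "no improvement in clinical findings, no change on MRI, no change in CSF parameters, or worsening in those findings". The vascular definition includes "worsening of clinical findings, no change or increase in acute phase response". None of these definitions mentions rescue, and neither do the analysis sets (8.1) or the primary and secondary analyses (8.4, 8.5).

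On who decides, 3.4 says "At the end of 1st month primary end point will be assessed by the physician" and 5.4 says "This will be an open-label, single arm study". Section 7.5 requires no adjudication committee.

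Section 5.5.8 disallows, for the whole study, corticosteroids at 20 mg/day or more (or above 0.4 mg/kg) and cyclophosphamide. Section 5.9.4 says the prednisolone dose should not go up during the trial. Section 5.5.9 stops study drug when a prohibited medication is used.

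**The concern.** The study has one arm and compares patients only with their own baseline. Section 8.4.2 sets a threshold for claiming efficacy: a 50% response in half the patients. If a patient improves by Day 30 because of pulse steroids, nothing in the design separates that from a canakinumab effect. The protocol already treats high-dose steroid as a confounder before baseline: it excludes pulse methylprednisolone in the past month and caps baseline prednisolone at 20 mg. It has no matching rule between Day 0 and Day 30.

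There is also a practical problem. A site treating a deteriorating patient finds one section prescribing a regimen and two sections disallowing its components.

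**Working it through.** There is no sample-size or power figure to reproduce: 8.7 gives 10 patients on exploratory grounds and 8.1 says the study is not powered. The check is a reading of the rules, plus arithmetic on size.

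**1. Can rescue act before the endpoint is read?** Assume the first pulse is on Day 7, with pulses on consecutive days. The Day 30 visit has a ±7-day window (5.7), so it falls on Day 23 to 37.

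| Regimen | Last pulse | Days to Day 30 | Range with window |
|---|---|---|---|
| Vascular, 3 days | Day 9 | 21 | 14–28 |
| Neurologic, 5 days | Day 11 | 19 | 12–26 |
| Neurologic, 10 days | Day 16 | 14 | 7–21 |

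So at least a week, and up to four, remains after the last pulse, with 1 mg/kg/day prednisolone continuing.

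**2. Does existing text settle the classification?**
- The no-deterioration condition in 2.1 is tied to Day 30. A patient who worsened in week 1 and then improved need not be worse than baseline at Day 30.
- Both non-response definitions include worsening, but neither says that worsening before rescue still counts after later improvement. The week-1 decision can also follow lack of response without worsening.
- Section 5.5.5 asks the physician to judge response to canakinumab. That permits non-response for a rescued patient but does not require it.
- Section 5.5.9 stops study drug but does not define that as non-response. The only dose before Day 30 is on Day 0.
- The intent-to-treat set (8.1) keeps every dosed patient. Nothing says whether protocol-directed rescue is a major deviation for the per-protocol set.

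**3. Which response classes are exposed?** Neurologic complete response needs full recovery, disappearance of MRI lesions and normal CSF. Vascular complete response needs 50% gains on the global VAS scores and CRP, with aneurysm size or calf swelling merely stable. Partial response is easier in both groups. Section 8.4.1 names complete responders; 8.4.2 does not say which class its rule counts.

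**4. Size.** One patient is 1/10 = 10 percentage points. The rule needs 5/10, so one reclassified patient turns 4/10 into 5/10 (5 − 4 = 1) and two turn 3/10 into 5/10 (5 − 3 = 2).

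As an illustration only, let X ~ Bin(10, p) and take P(X ≥ 5), where a further 10% of patients are rescued and classed as responders:

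| Assumed response without rescue | P, rescue = non-response | P, rescue ignored |
|---|---|---|
| 10% | 0.002 | 0.033 |
| 20% | 0.033 | 0.150 |
| 30% | 0.150 | 0.367 |
| 40% | 0.367 | 0.623 |
| 60% | 0.834 | 0.953 |

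If instead 20% are rescued and 50–80% of those are classed as responders, a 30% base gives p = 0.30 + 0.20 × 0.5 = 0.40 to 0.30 + 0.20 × 0.8 = 0.46, and the probability rises from 0.150 to 0.367–0.522.

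**5. Conflict with 5.5.8 and 5.9.4.** Rescue prednisolone is 1 / 0.4 = 2.5 times the weight-based limit at any weight, and 1 mg/kg reaches 20 mg/day at 20 kg, so any adult passes both limits. Cyclophosphamide is listed by name. A rescued patient who looks improved at Day 30 would continue dosing under 5.5.5 but stop under 5.5.9.

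**6. Follow-up.** Section 5.7 schedules patients who stop study drug for a visit 8 weeks (±1 week) after the last dose. After the Day 0 dose that is Day 56 (49–63). No rule covers a Day 30 assessment missed for this reason.

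**The case against.** The best defence is that a sensible physician would class these patients correctly. The fixed regimen is for worsening patients, the week-1 decision needs repeat imaging or CSF so failure is documented, both non-response definitions include worsening, and 5.5.5 refers to response to canakinumab. This narrows the route but leaves the choice open, with an unblinded assessor and no adjudication.

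Second, 8.4.1 also lists achievement of steroid tapering, and 5.9.4 expects no more than 5 mg/day at Day 120. A patient put on 1 mg/kg/day would tend to count against canakinumab there. That stands, but it does not correct the responder percentage.

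Third, 5.5.8 may only list what cannot be combined with continued canakinumab. On that reading 5.5.6 and 5.5.9 are compatible, provided rescue ends study drug. This is reasonable, but 5.5.8 and 5.9.4 do not say it.

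Fourth, this is a 10-patient pilot and medications are recorded, so a reader with individual data could reclassify. That lowers the severity; it does not supply the missing rule.

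**Conclusion.** The gap is real and should be fixed, though the exploratory purpose keeps it from being critical. Compared with counting rescue as non-response, ignoring it can only leave the responder percentage unchanged or raise it, by 10 points per patient affected. The risk is greatest for vascular response and for partial response, and lower for neurologic complete response.

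A reader might infer three stronger claims that the documents do not support:
- That the plan counts rescued patients as responders. It is silent, and non-response is permitted.
- That the chance of meeting the 50% rule is inflated by a known amount. No rescue rate or response rate is given, and the probabilities above depend heavily on the assumed base rate.
- That 5.5.8 plainly bans methylprednisolone pulses by name after baseline. That line refers to the last month and may apply before baseline only. The conflict rests on the general corticosteroid limit, the cyclophosphamide entry and 5.9.4.

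**What to change.** Add to 2.1, 5.9.1 and 8.4: *A patient who receives rescue for BD under 5.5.6 (IV methylprednisolone, prednisolone above the baseline dose, or cyclophosphamide) on or before the Day 30 assessment is a non-responder in the primary analysis, whatever the Day 30 findings. A sensitivity analysis ignores rescue.* State that such patients are still assessed at Day 30, and that the 8-week visit in 5.7 is additional.

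Add to 5.5.8 and 5.9.4 a cross-reference that rescue under 5.5.6 may be given as treatment. The sponsor should then say whether rescue triggers discontinuation under 5.5.9, as the current text implies, or is exempt. That is a design choice affecting all 12 months: secondary endpoints count exacerbations over that period, so either answer is defensible. Also say whether the methylprednisolone line in 5.5.8 applies before baseline only.

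No new data are needed: 5.5.7 records all medications and the assessment schedule covers steroid use at every visit. The cost is a possibly lower reported response rate, including patients rescued early who might have responded later. The sensitivity analysis shows the other bound.
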